8.4.1 Laboratory evaluations

A local laboratory will be used for analysis of all specimens collected.

All abnormal lab results must be evaluated for criteria defining the inclusion/exclusion criteria, an adverse event and reported as such if the criteria are met. For those lab adverse events, repeated evaluations are mandatory until normalization of the result(s) or until the result is no longer considered to be clinically significant.

Table 8-4 Laboratory Assessments

Test Category	Test Name
Hematology	Hemoglobin, hematocrit, red blood cell (RBC) count, white blood cell (WBC) count with differentials and platelet count. Coagulation testing including prothrombin time (PT) (also reported as INR), activated partial thromboplastin time (aPTT) and fibrinogen Commercially Confidential Information
Chemistry	Sodium, potassium, creatinine, BUN or urea, uric acid, chloride, albumin, calcium, magnesium, alkaline phosphatase, total bilirubin (direct and indirect), bicarbonate/HCO ₃ , LDH, GGT, AST, ALT, amylase, lipase, CK, glucose, total cholesterol, triglycerides, total protein, C-reactive protein (CRP). Globulin and albumin/globulin ratio Commercially Confidential Information
Urinalysis	Dipstick measurements for bilirubin, blood, glucose, ketones, leukocytes, nitrite, pH, protein, specific gravity, urobilinogen. If dipstick measurement results are positive (abnormal), results will be captured in the CRF. Microscopy must be assessed following an abnormal dipstick test with results captured in the CRF. Commercially Confidential Information
Pregnancy / FSH Test	Serum / Urine pregnancy test and FSH levels (see Section 8.4.4) Commercially Confidential Information

8.4.2 Electrocardiogram (ECG)

For Part A, triplicate ECGs will be collected at screening, baseline, and at Day 8 (EOS). At other times, single ECGs will be collected at all times when PK samples are collected (ECG is not needed at 2 min).

For Part B, triplicate ECGs will be collected at screening, baseline, Days 3, 4, and Day 12 (EOS). At other times, single ECGs will be collected at all times when PK samples are collected (ECG is not needed at 2 min).

All ECGs will be measured after a 10 min rest in the supine position. The following parameters will be reported : PR interval, QRS duration, heart rate, RR interval, QT interval, QTcF.

The Fridericia QT correction formula (QTcF) must be used for clinical decisions.

As applicable, QTcF and QTcB may be calculated at the site. Unless auto-calculated by the ECG machine, the investigator must calculate QTcF at the Screening and/or Baseline visit(s) (as applicable) to assess eligibility and continuation in the study.

Clinically significant abnormalities must be recorded on the relevant section of the medical history/Current medical conditions/AE eCRF as appropriate.

8.4.3 Holter ECG Monitoring

25-hour Holter monitoring will be conducted on specified days to collect ECG data for QTcF assessment. These data will not immediately be visible to the site investigator and staff. The Holter recordings will be transmitted to the selected ECG core laboratory for analysis. ECG extractions for QTcF analysis will be taken at the same nominal timepoints as the PK draws. All ECGs will be measured after a 10 min rest in the supine position prior to the PK draws.

In Part A, continuous 12 lead ECG Holter monitoring will be performed for 25 hours on Day 1 from 1 hour pre-dose through 24 hours post-dose.

In Part B, continuous 12 lead ECG Holter monitoring will be performed for 24 hours on Days 1 and 5 from 1 hour pre-dose through 24 hours post-dose.

Full details of all procedures relating to the ECG collection are contained in the SOM and/or Holter monitoring manual.

8.4.4 Pregnancy and assessments of fertility

All women will have pregnancy testing. Additional pregnancy testing might be performed if requested by local requirements.

At screening and at the end of the study, serum pregnancy test should be performed, while during the study duration urinary pregnancy tests are sufficient. In case the pregnancy urine test is positive, the result needs to be confirmed with serum test.

Assessments of Fertility

Medical documentation of oophorectomy, hysterectomy, or tubal ligation must be retained as source documents. Subsequent hormone level assessment to confirm the woman is not of child-bearing potential must also be available as source documentation in the following cases:

1. Surgical bilateral oophorectomy without a hysterectomy
2. Reported 12 months of natural (spontaneous) amenorrhea with an appropriate clinical profile.

In the absence of the above medical documentation, FSH testing is required of any female subject regardless of reported reproductive/menopausal status at screening/baseline.

8.4.5 Appropriateness of safety measurements

The safety assessments selected are standard for this subject population.

8.5 Additional assessments

Additional assessments are specified below with the Assessment Schedule ([Table 8-1](#) and [Table 8-2](#)) detailing when each assessment is to be performed.

The methods for each assessment and data recording details are specified in the SOM.

8.5.1 Pharmacokinetics

PK samples will be collected at the visits defined in the Assessment Schedule ([Table 8-1](#) and [Table 8-2](#)). Follow instructions outlined in the SOM regarding sample collection, numbering, processing, and shipment. See the potential use of residual samples for more information.

Commercially Confidential Information

PK samples will be obtained from all subjects, but only samples from KAE609 treated subjects will be analyzed.

Commercially Confidential Information

For standard PK abbreviations and definitions see the list provided at the beginning of this protocol.

The following PK parameters will be determined using the actual recorded sampling times and non-compartmental method(s) with Phoenix WinNonlin (Version 8 or higher): For SAD: C(0), C_{max}, T_{max}, AUC_{0-24h}, AUC_{last}, AUC_{inf}, T_{1/2}, V_{ss} and CL and for MAD: C_{max}, T_{max}, AUC_{0-24h}, C_{trough}, AUC_{tau} etc. as applicable from the plasma concentration-time data.

The linear trapezoidal rule will be used for AUC calculation. Regression analysis of the terminal plasma elimination phase for the determination of T_{1/2} will include at least 3 data points after C_{max}. If the adjusted R² value of the regression analysis of the terminal phase will be less than 0.75, no values will be reported for T_{1/2}, AUC_{inf}, V_{ss} and CL.

Commercially Confidential Information

Commercially Confidential Information

9 Study discontinuation and completion

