1.2 Purpose

The purpose of this study is to assess the safety and tolerability and pharmacokinetics (PK) of single ascending doses (SAD) and multiple ascending doses (MAD) of KAE609 administered by iv infusion in healthy subjects, to support further clinical development of KAE609 in patients with severe malaria and to guide dose selection for future trials.

2 Objectives and endpoints

Table 2-1 Objectives and related endpoints

Objective(s)	Endpoint(s)
Primary objective(s)	Endpoint(s) for primary objective(s)

 To assess the safety and tolerability of single and multiple iv doses of KAE609 in healthy subjects 	
 Adverse events, physical examination findings, vital signs, ECG findings (including QTcF), safety laboratory assessments including chemistry, hematology, and urinalysis results
Secondary objective(s)	Endpoint(s) for secondary objective(s)

 To assess the pharmacokinetics (PK) of single and multiple iv doses of KAE609 in healthy subjects 	
 AUC, Tmax, Cmax, CL, Vz, and T1/2

 To assess local tolerance at infusion site of KAE609 iv administration 	
 Findings of physical examination of infusion site

Commercially Confidential Information

3 Study design

This is a randomized, subject and investigator-blinded, placebo-controlled, single and multiple ascending iv dose study in healthy subjects. The study consists of two parts and the study scheme is shown in [Figure 3-1](#):

- Part A is a single ascending dose (SAD) study with 5 cohorts of 8 subjects each
- Part B is a multiple ascending dose (MAD) study with 2 cohorts of 9 subjects each

For both parts of the study, each subject will participate in an up to 28- day screening period during which a full physical examination, medical history, drug screening, vital signs, ECG evaluation and safety laboratory tests evaluation will be performed.

A review of safety and PK data will be conducted at the completion of each cohort prior to dosing of the next subsequent cohort. Please also refer to [Section 6.5.1](#) for more details on dose escalations. Safety assessments will include physical examinations, ECGs, vital signs, standard clinical laboratory evaluations (hematology, blood chemistry, urinalysis) adverse event and serious adverse event monitoring.

Commercially Confidential Information

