4.2 Rationale for dose/regimen and duration of treatment

Commercially Confidential Information

Following completion of each cohort, apart from safety, available PK data will be reviewed to confirm the predictions and to keep the exposure within the AUC and Cmax considered safe

Commercially Confidential Information

Starting dose

Commercially Confidential Information

Dose escalation

Commercially Confidential Information

Highest dose

Commercially Confidential Information

Commercially Confidential Information

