6.7 Preparation and dispensation

Each study site will be supplied with study drug in packaging as described under the investigational and control drugs section (Section 6.1.1).

KAE609 will be administered to the subject at the study center via the following route of administration:

- iv bolus administration over approximately 2 min (cohorts A1, A2 and B1)
- iv infusion over approximately 10 min (cohorts A3, A4, A5 and B2)

Depending on emerging data of this study infusion duration might be adapted (for example infusion over 10 min instead of bolus injection).

See the SOM and Pharmacy Manual for further details.

7 Informed consent procedures

Eligible subjects may only be included in the study after providing (witnessed, where required by law or regulation), IRB/IEC-approved informed consent.

Informed consent must be obtained before conducting any study-specific procedures (e.g. all of the procedures described in the protocol). The process of obtaining informed consent must be documented in the subject source documents.

Novartis will review the investigators/CRO proposed informed consent form to ensure it complies with the ICH E6 GCP guidelines and regulatory requirements and is considered appropriate for this study. Any further changes to the proposed consent form suggested by the investigator must be agreed to by Novartis before submission to the IRB/IEC.

Information about common side effects already known about the investigational drug can be found in the Investigator's Brochure. This information will be included in the subject informed consent and should be discussed with the subject during the study as needed. Any new information regarding the safety profile of the investigational drug that is identified between Investigator's Brochure updates will be communicated as appropriate, for example, via an investigator notification or an aggregate safety finding. New information might require an update to the informed consent and then must be discussed with the subject.

Male subjects must be informed that if a female partner becomes pregnant while he is enrolled in the study, contact with the female partner will be attempted to request her consent to collect pregnancy outcome information.

Commercially Confidential Information

A copy of the approved version of all consent forms must be provided to Novartis/sponsor after IRB/IEC approval.

Refer to the SOM for a complete list of ICFs included in this study.

8 Visit schedule and assessments

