Assessment schedule lists all of the assessments and indicates with an “X”, the visits when they are performed. All data obtained from these assessments must be supported in the subject’s source documentation.

Subjects should be seen for all visits/assessments as outlined in the assessment schedule or as close to the designated day/time as possible. Missed or rescheduled visits should not lead to automatic discontinuation. Subjects who prematurely discontinue the study for any reason should be scheduled for a visit as soon as possible, at which time all of the assessments listed for the EOS visit will be performed. At this EOS visit, the adverse event and concomitant medications should be recorded on the CRF.

Specification and timing of each assessment are detailed in the protocol. The methods and recording of each assessment may be outlined in the SOM.

Epoch	Screening		Treatment Period										Post-Treatment Follow-Up					Post Study	
Visit Name	Screening	Baseline	Treatment										Follow-up				EOS	Safety Contact	
Days	-29 to -2	-1	1										2	3	4	6	8	30	
Time (post-dose)	-	-	-1h ¹	0h	2min ²	10min	30min	1h	3h	4h	6h	12h	24h	48h	72h	120h	-	-	
12 lead Holter continuous ECG ⁸			X																
ECG evaluation ⁴	X	X	X			X	X	X	X		X	X	X				X		
Blood Pressure and Pulse Rate	X	X	X			X	X	X	X				X		X		X		
Drug administration record ⁷				X															
Injection/infusion site observation			X		X		X												
Blood chemistry	X	X											X		X		X		
Hematology	X	X											X		X		X		
Urinalysis	X	X											X				X		
PK blood collection			X		X	X	X	X	X		X	X	X	X	X	X	X		
CCI			X																
CCI			X																
Inpatient			X																
Concomitant medications	X ¹⁰																		
Adverse events/serious adverse events	X ¹⁰																		

Epoch	Screening		Treatment Period										Post-Treatment Follow-Up					Post Study	
Visit Name	Screening	Baseline	Treatment										Follow-up				EOS	Safety Contact	
Days	-29 to -2	-1	1										2	3	4	6	8	30	
Time (post-dose)	-	-	-1h ¹	0h	2min ²	10min	30min	1h	3h	4h	6h	12h	24h	48h	72h	120h	-	-	
Study completion information																		X	
Safety Follow up Call																			S

^X Assessment to be recorded in the clinical database or received electronically from a vendor

^S Assessment to be recorded in the source documentation only

¹ Pre-dose

² Only collected/done in cohorts with bolus injection.

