5.3.2 Graphical presentation of results

Arithmetic mean (SD) plasma concentration data will be plotted across time, with separate line types for each treatment.

Overlying individual plasma concentration-time profiles will be generated.

Scatterplots of Cmax and AUC parameters versus dose will be created with the estimated power model curve overlaid.

6 Statistical methods for Pharmacodynamic (PD) parameters

Not applicable.

7 Statistical methods for safety and tolerability data

The primary objective of this study is to assess the safety and tolerability of single and multiple ascending iv doses of KAE609 in healthy subjects.

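### The linear trapezoidal rule in protocol 8.5.1 is likely to overstate AUC by a few percent after iv dosing; separately, Vz is the declared endpoint but only Vss is planned

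*Protocol*

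**What the plan says.** On the AUC rule, protocol 8.5.1 reads "The linear trapezoidal rule will be used for AUC calculation". It makes no exception for falling concentrations, and the readable SAP gives no rule of its own. Protocol 6.7 gives cohorts A1, A2 and B1 a bolus over about 2 min; the others receive "iv infusion over approximately 10 min (cohorts A3, A4, A5 and B2"). The "PK blood collection" row of Table 8-1 (Part A) has samples pre-dose, at 2 min (bolus cohorts only), 10 min, 30 min, 1, 3, 6, 12, 24, 48, 72 and 120 h, and on Day 8.

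AUC is used in three visible places: the descriptive summaries, the between-cohort review in protocol 4.2 ("available PK data will be reviewed to confirm the predictions and to keep the exposure within the AUC and Cmax considered safe"), and SAP 5.3.2 ("Scatterplots of Cmax and AUC parameters versus dose will be created with the estimated power model curve overlaid").

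On the volume parameter, protocol Table 2-1 and SAP 1.3 give the same secondary PK endpoints: "AUC, Tmax, Cmax, CL, Vz, and T1/2". The derivation list in 8.5.1 reads "For SAD: C(0), C_{max}, T_{max}, AUC_{0-24h}, AUC_{last}, AUC_{inf}, T_{1/2}, V_{ss} and CL", and then "for MAD: C_{max}, T_{max}, AUC_{0-24h}, C_{trough}, AUC_{tau} etc. as applicable". The adjusted R² rule in 8.5.1 withholds Vss, not Vz, when the terminal fit is poor. Table 12-1 defines Vss only, and SAP 5.1 lists Vss for both parts.

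**The concern.** After a short iv input the concentration falls over almost the whole sampling period, and the sampling intervals widen to 24 and 48 h. On each convex interval the linear rule adds area that is not there. That error is systematic, so more subjects do not reduce it. AUC and CL are declared secondary endpoints, and the study is meant to guide dose selection for later trials, so their absolute values have some use beyond this report.

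The volume mismatch is a matter of consistency. A reader of Table 2-1 expects Vz, but the visible text never lists, defines or gives a reporting rule for it. Vz and Vss are different quantities when disposition has more than one exponential phase.

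**Working it through.** The plan states no AUC error, half-life or quantification limit, so there is no figure of its own to reproduce.

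**One interval by hand.** For a mono-exponential fall from 1 over an interval of length d with half-life h, let x = ln 2 × d/h. The exact area per unit time is (1 − e^−x)/x; the linear rule gives (1 + e^−x)/2.
- d = h: exact 0.5/0.693 = 0.721, linear 0.750, error 0.750/0.721 − 1 = +4.0%.
- d = 2h: exact 0.75/1.386 = 0.541, linear 0.625, error +15.5%.

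If the half-life were 24 h (assumed), the 72 to 120 h interval would be the second case. The logarithmic rule is exact for a mono-exponential fall.

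**Whole profile.**
- From the documents: a 10-min infusion (6.7) and the Part A times (Table 8-1), with Day 8 taken as 168 h.
- Assumed: noise-free bi-exponential disposition; terminal half-life 6, 8, 12, 18, 24, 36 or 48 h; distribution half-life 0.17, 0.25, 0.5, 1, 2 or 3 h; fast fraction 0.5 to 0.9 in steps of 0.1. That is 7 × 6 × 5 = 210 cases.
- Assumed quantification limit: none, 0.1, 0.5 or 1% of the highest sampled concentration.
- AUCinf = AUClast + Clast/λz, with λz from the last three usable points, compared with the exact integral.

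Table 8-1 heads its time row as post-dose and does not say whether the clock starts at the beginning or the end of a 10-min infusion. Both readings were run.

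| | Times from start of dosing | Times from end of infusion |
|---|---|---|
| Linear AUCinf error, median (lowest to highest over the four limits) | about +4 to +6% | about +2 to +4% |
| Linear AUCinf error, full range | +1.4 to +12.4% | −3.1 to +6.6% |
| Linear AUC0-24h error, no limit, median (range) | +3.4% (+0.3 to +10.7) | +1.1% (−3.3 to +5.3); negative in 56 of 210 |
| Log-down closer to true AUCinf | 208 to 210 of 210 | 175 to 198 of 210 |
| Log-down for AUC0-24h, no limit | median error 1.2% (0.2 to 3.5) | closer in 120 of 210; error reaches −7.6% |

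Under the second reading the first sample falls 10 min after the infusion ends. The straight line from zero to that sample cuts off part of the peak, and this loss offsets some of the gain on the declining intervals. Both rules share the loss.

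**CL.** Since CL = dose/AUCinf, the median error without a quantification limit is 1/1.055 − 1 = −5.2% under the first reading and 1/1.039 − 1 = −3.8% under the second.

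**Dose comparison.** With times from the start of dosing, a fixed assay limit and an assumed 4- to 20-fold dose range, the power-model slope for AUCinf shifts by a median below 0.01 and at most 0.04.

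**Vz against Vss.** Vz/Vss = (1/λz)/MRT. With assumed half-lives of 0.5 and 24 h and 10% of AUC in the fast phase, the ratio is 24/(0.1 × 0.5 + 0.9 × 24) = 24/21.65 = 1.11. With 30% it is 24/(0.3 × 0.5 + 0.7 × 24) = 24/16.95 = 1.42. On the grid it runs from 1.00 to 2.08 (median 1.10) and exceeds 1.2 in 30% of cases.

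**The case against.** The linear rule is prespecified and clearly stated, and nothing in the SAP contradicts it. The visible PK analysis consists of listings, descriptive statistics and a power-model plot, and no visible test or threshold depends on a few percent of AUC. Sampling error is probably larger than the bias. With 6 active subjects per cohort and an assumed between-subject CV of 20 to 40%, the standard error of a log geometric mean, √(ln(1 + CV²)/6), is about 0.08 to 0.16, or roughly 8 to 16%. If the exposure limits behind section 4.2 came from the linear rule, keeping it preserves comparability; that text is redacted. All of this stands, and it is why the point is an inexpensive improvement and not an error in the plan.

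A reader might infer that the net error always has the same sign, or that one software setting removes most of it. The documents do not support either statement, because they leave the time origin open. If times run from the end of infusion, the net linear error is sometimes negative, and for AUC0-24h the log rule has no clear advantage. The sign is certain only for each convex declining interval. The medians and case counts describe an assumed, equally weighted grid; they are not probabilities for KAE609.

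On the volume parameter, it can fairly be said that nothing is lost: Vz = CL × T1/2/ln 2, SAP 5.1 plans both CL and T1/2 in each part, and the 8.5.1 MAD list is open-ended. That removes any fear of an unrecoverable endpoint, but it does not make the endpoint table agree with the lists.

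**Conclusion.** Both parts hold, as minor points.

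(1) The stated rule overstates area on the convex declining intervals that make up nearly all of an iv profile. For Part A infusion cohorts this suggests an AUCinf error of a few percent upward, with CL too low by a similar proportion, under either time origin. The size rests on assumed half-lives, fast fractions and quantification limits. Linear-up/log-down improves AUCinf and CL in most cases under both readings; for AUC0-24h the improvement is clear only if times run from the start of dosing. It would be wrong to conclude that dose proportionality or the between-cohort review is compromised: the slope hardly moves, and no visible decision depends on the difference. Part B was not computed, because the body of Table 8-2 is not readable.

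(2) The Vz/Vss mismatch needs no assumption. Table 2-1 and SAP 1.3 name one volume; the 8.5.1 SAD list and R² rule, Table 12-1 and SAP 5.1 name another. As written, a declared secondary endpoint has no planned derivation in the visible text.

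**What to change.** In protocol 8.5.1, replace the rule with linear-up/log-down: linear trapezoids while concentrations rise, logarithmic trapezoids while they fall. Report the linear AUC as a supplementary value if comparison with earlier data or with exposure limits is needed. The cost is one software setting and a few words, with no new samples. The downside is a possible second set of AUCs and differences of a few percent from any earlier linear-rule values.

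For the volume parameter, do one of two things:
- add Vz (CL/λz) to 8.5.1, including the adjusted R² rule, and to Table 12-1 and SAP 5.1; or
- change the endpoint to Vss in Table 2-1 and SAP 1.3.

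Either is a text edit only.

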12.5.1 Pharmacokinetics

For each part, KAE609 plasma concentration data will be listed by subject, and visit/sampling time point. Descriptive summary statistics will be provided by treatment and visit/sampling time point, Commercially Confidential Information

Summary statistics will include mean (arithmetic and geometric), SD, CV (arithmetic and geometric), median, minimum and maximum. Commercially Confidential Information

PK parameters will be listed by subject. Descriptive summary statistics will include mean (arithmetic and geometric), SD, and CV (arithmetic and geometric), median, minimum and maximum. An exception to this is Tmax where median, minimum and maximum will be presented.

Commercially Confidential Information

PK concentration data from this study may be used for population PK modeling. If performed, the results will be reported separately.

Table 12-1 Non-compartmental pharmacokinetic parameters

AUC0-t	The AUC from time zero to time t (e.g. 24h) (mass x time x volume-1)
AUClast	The AUC from time zero to the last measurable concentration sampling time (tlast) (mass x time x volume-1)
AUCinf	The AUC from time zero to infinity (mass x time x volume-1)
AUCtau	The AUC calculated to the end of a dosing interval (tau) at steady-state (amount x time x volume-1)
Cmax	The maximum (peak) observed plasma, blood, serum, or other body fluid drug concentration after single dose administration (mass x volume-1)
Tmax	The time to reach maximum (peak) plasma, blood, serum, or other body fluid drug concentration after single dose administration (time)
T1/2	The elimination half-life associated with the terminal slope (lz) of a semi logarithmic concentration-time curve (time). Use qualifier for other half-lives
CL	The total body clearance of drug from the plasma (volume x time-1)
Vss	The apparent volume of distribution at steady state from an intravenously administered dose (volume)

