5.1 Variables

The pharmacokinetic parameters are described as follows and will be calculated separately from the KAE609 concentration data:

- Part A (SAD): C_{max}, T_{max}, AUC_{last}, AUC_{inf}, AUC_{0-t} (AUC₀₋₂₄), T_{1/2}, V_{ss} and CL
- Part B (MAD): C_{max}, T_{max}, AUC_{0-24h}, T_{1/2} Day 1 and C_{max}, T_{max}, AUC_{tau} (AUC₀₋₂₄), AUC_{last}, T_{1/2}, V_{ss} and CL

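### The adjusted R-squared rule in Protocol 8.5.1 would withhold Part B clearance on a terminal-slope criterion that dose/AUCtau does not use

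*Protocol*

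**What the plan says.** **The rule.** Protocol 8.5.1 lists the parameters for the single-dose and multiple-dose parts, asks for at least three points after Cmax in the terminal regression, and then sets one threshold. If the adjusted R-squared "value of the regression analysis of the terminal phase will be less than 0.75, no values will be reported for" T1/2, AUCinf, Vss and CL. Nothing visible limits this to Part A. AUCtau, AUC0-24h and AUClast are not withheld.

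**CL as an endpoint.** Protocol Table 2-1 gives "AUC, Tmax, Cmax, CL, Vz, and T1/2" as the endpoints for the PK objective, which covers single and multiple doses together.

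**CL in Part B.** The multiple-dose list in Protocol 8.5.1 does not name CL but is left open: "for MAD: C_{max}, T_{max}, AUC_{0-24h}, C_{trough}, AUC_{tau} etc. as applicable". SAP 5.1 does name it. Its Part B entry has a Day 1 group without CL, then a second group that ends "AUC_{tau} (AUC₀₋₂₄), AUC_{last}, T_{1/2}, V_{ss} and CL". AUCinf appears in the SAP for Part A only.

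**Definitions.** Protocol Table 12-1 defines AUCtau as "The AUC calculated to the end of a dosing interval (tau) at steady-state" and CL as "The total body clearance of drug from the plasma". Neither document shows a formula for CL. The visible SAP text does not repeat the adjusted R-squared rule.

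**The concern.** In Part A, CL is naturally dose/AUCinf. AUCinf includes an extrapolated tail that depends on the terminal slope, so a rule on the quality of that fit is relevant there.

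AUCtau is an area observed within one dosing interval, and dose/AUCtau uses no slope. A rule that withholds it because the terminal regression fits poorly tests the wrong thing. The plan would then report a subject's AUCtau and suppress the CL that follows from it by one division.

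At stake is the completeness of the Part B summary of a secondary endpoint, in cohorts with six active subjects each. What Part B CL does depend on is whether steady state has been reached by the fifth dose, and the visible plan attaches no such check to it.

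**Working it through.** No figure in the plan bears on this rule, so there is none to reproduce first.

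**Inputs from the documents**
- Threshold 0.75 and a minimum of 3 points (Protocol 8.5.1).
- Part B: five doses at 24 h intervals (Protocol 3).
- Six active subjects per cohort (Protocol 12.8.1).
- Part A PK samples at 24, 48, 72 and 120 h and at the Day 8 visit, about 168 h (Protocol 8, Part A schedule). The Part B schedule is not in the text.

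**Assumed, because the documents do not show them:** half-life, assay variability, quantification limit, and linear one-compartment kinetics.

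**1. Which parameters need the slope**

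| Parameter | Needs terminal slope? | Withheld by the rule? |
|---|---|---|
| T1/2, AUCinf, Vss | Yes | Yes |
| CL, Part A (dose/AUCinf) | Yes | Yes |
| CL, Part B (dose/AUCtau) | No | Yes, as worded |
| AUCtau | No | No |

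The third row is the mismatch.

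**2. What the threshold means.** Adjusted R² = 1 − (1 − R²)(n − 1)/(n − 2). With n = 3 this is 1 − 2(1 − R²), so a value below 0.75 means R² below 0.875.

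**3. Size per withheld value.** 1/6 = 17% of a cohort's CL data.

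**4. How good dose/AUCtau is after five doses.** Relative to single-dose AUCinf, AUCtau after dose 5 is 1 − 2^(−120/T), where T is the half-life in hours. CL is overstated by the reciprocal of that fraction, minus 1.
- T = 12: fraction 0.999, overstatement 0.1%.
- T = 24: 1 − 2^(−5) = 0.969, overstatement 3%.
- T = 48: 1 − 2^(−2.5) = 0.823, overstatement 21%.
- T = 72: 1 − 2^(−1.667) = 0.685, overstatement 46%.

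**5. How often the rule would trigger.** Simulated mono-exponential profiles with log-normal error show how far the answer depends on unseen inputs. At 20% CV, fitting three points:

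| Points used | T = 24 h | T = 48 h |
|---|---|---|
| 24, 48, 72 h | 8% | 38% |
| 72, 120, 168 h (last three Part A times) | about 0% | 8% |
| Last three of a 24 h window | 51% | 70% |

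The second row assumes all three samples are quantifiable. At one half-life and one error level, the rate runs from about 0% to 51% on sampling alone. Choosing the best-fitting set of points instead of the last three lowers it further: at T = 72 h, 20% CV, sampling to 168 h and a quantification limit of 0.1% of the initial concentration, from 24% to about 1%.

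**The case against.** **The rule was meant for Part A.** The four withheld parameters all stand in the protocol's single-dose list, and its multiple-dose list names none of them. Redacted blocks also follow the rule in 8.5.1, so an unseen qualification is possible. The intent may well have been single-dose only. But the visible wording does not say so, the multiple-dose list is open-ended, and SAP 5.1 names CL for Part B.

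**The formula is an inference.** This stands: neither document defines Part B CL as dose/AUCtau. It is the natural reading, because AUCinf is not listed for Part B. Nor would dose/AUCinf after the fifth dose work, because that area carries drug from earlier doses. At a 24 h half-life it would be (1 − 2^(−5))/(1 − 2^(−1)) = 0.969/0.5 = 1.94 times the single-dose area. If something else was intended, the formula still has to be stated.

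**Nothing is lost.** This stands. AUCtau is still reported, parameters are listed by subject, and the Part B doses are fixed, so a reader could divide. What is affected is the reported value and the planned CL summary.

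**A tempting stronger reading** is that the rule selectively drops slow eliminators and so biases mean CL upward. The documents do not support it. The direction is plausible when half-life is long relative to sampling, but half-life and assay error are not shown. Fast eliminators close to the quantification limit can fail too: in one run (30% CV, limit at 1% of the initial concentration, last three points) 7% failed at a 6 h half-life against 2.5% at 12 h. At the long half-lives where the rule triggers most, dose/AUCtau after five doses is not a valid steady-state clearance either.

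**Conclusion.** The point holds as a defect in a reporting rule. As worded, the rule covers CL in both parts, the SAP plans CL for Part B, and the adequacy of the terminal fit has no bearing on dose/AUCtau. This rests on Part B CL being dose/AUCtau, which the SAP list implies but does not state, and on no qualification in the redacted text.

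The size is 17% of a cohort's CL values per withheld subject. The number of subjects affected in Part B cannot be given. A reader might infer that a secondary endpoint is lost, or that its mean is biased. Neither follows: CL can be recovered from AUCtau, and the selection claim depends on quantities that the documents do not show. Reporting Part B CL regardless of fit is sound only where steady state is reached, and the overstatement of 3% to 46% over half-lives of 24 to 72 h shows why a check is needed.

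**What to change.** In Protocol 8.5.1, limit the adjusted R-squared rule to parameters that use the terminal slope: T1/2, AUCinf, Vss and Part A CL.

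In Protocol 8.5.1 and SAP 5.1:
- Define Part B CL as dose/AUCtau on the last dosing day, and report it regardless of adjusted R-squared.
- Add a steady-state check from the Ctrough values already planned, and flag CL where it is not met. Under the same one-compartment assumption, the rise between the troughs after doses 4 and 5 is (1 − 2^(−120/T))/(1 − 2^(−96/T)) − 1, which is 3%, 10% and 14% at 24, 48 and 72 h. That is small against assay noise in one subject, so the check should use the cohort's troughs over all days sampled.
- Report the number of withheld values per parameter and cohort, out of 6.

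The cost is a few sentences and one extra table line, with no new data. The small downside is that flagged CL values will overstate clearance if steady state is not reached by dose 5, so they must be read as such.
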